8.3.3 CLASSIFICATION OF AN ADVERSE EVENT

8.3.3.1 SEVERITY OF EVENT

For AEs not included in the protocol-defined grading system, they must be determined to be Serious or Non-serious, using the definitions in sections 8.3.1 and 8.3.2.

8.3.3.2 RELATIONSHIP TO STUDY INTERVENTION

A determination of the adverse event's relation to the study product will be made by the investigator based on temporal relationship and clinical judgement. The degree of certainty about association will be graded using the World Health Organization's Uppsala Monitoring Centre categories below. In a clinical trial, the study product must always be given consideration.

- **Certain** – The AE occurs in a plausible temporal relationship with the study intervention and cannot be explained by concurrent disease or other drugs.
- **Probable** – The AE occurs in a reasonable time sequence with the study intervention and unlikely to be explained by concurrent disease or other drugs.
- **Possible** – The AE occurs in a reasonable time sequence with the study intervention but could be explained by concurrent disease or other drugs.
- **Unlikely** – The AE occurs in a temporal relationship with the study intervention that makes a causal relationship improbable and concurrent disease and/or other drugs provide plausible explanations.

Regardless of the investigator's decision, patients should continue to be followed through Month 12.

8.3.3.3 EXPECTEDNESS

The Medical Monitor will be responsible for determining whether an AE is expected or unexpected. An AE will be considered unexpected if the nature, severity, or frequency of the event is not consistent with the information about adalimumab provided in the Summary of Product Characteristics (SmPC).

8.3.4 TIME PERIOD AND FREQUENCY FOR EVENT ASSESSMENT AND FOLLOW-UP

The occurrence of an AE or SAE (encompassing serious adverse reactions, SARs, and suspected unexpected serious adverse reactions, SUSARs, in the UK) may come to the attention of study personnel during study visits and interviews of a study participant presenting for medical care, or upon review by a study monitor.

All AEs including local and systemic reactions will be captured on **Adverse Event Checklist**. All AEs that occur during the study must be documented appropriately regardless of relationship and will be categorized as either serious or non-serious. All AEs will be followed to adequate resolution.

Any medical condition present at the time that the participant is screened will be considered as baseline and not reported as an AE. However, if the study participant's condition deteriorates at any time during the study, it will be recorded as an AE.

The study coordinator will record all reportable events with start dates occurring any time after informed consent is obtained until 70 days after the last day of study participation and the last dose of study medication. At each study visit, the study coordinator will ask about the occurrence of AE/SAEs

since the last visit. Events will be recorded on **Adverse Event Checklist** at each visit and followed for outcome information until resolution or stabilization.

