4 STUDY DESIGN

4.1 OVERALL DESIGN

Hypotheses for this trial include:

- 1) Patients who stop adalimumab will have a shorter time to uveitis recurrence compared to those who continue treatment. Patients randomized to continue treatment will have a higher rate of adverse events compared to patients randomized to stop treatment.
- 2) Patients with higher serum levels of MRP8/14, higher ESR, higher ADA, and higher CRP will have a higher uveitis recurrence rate compared to patients with lower serum levels. In addition, period of inactive uveitis, age at randomization, and duration of adalimumab treatment before randomization will be associated with uveitis recurrence rate.
- 3) A smaller proportion of patients who stop adalimumab will have controlled ocular inflammation at Month 6 and Month 12 compared with patients who never stop adalimumab. In addition, among patients who stop adalimumab and have a uveitis recurrence, anti-adalimumab antibodies will be associated with a longer time to regaining uveitis control after restarting treatment. MRP8/14 levels will be associated with the likelihood of establishing control of ocular inflammation after restarting adalimumab treatment following uveitis recurrence.

This study is a phase IV clinical trial.

The study design is a multicenter, randomized, placebo-controlled, superiority trial comparing stopping adalimumab treatment to continuing adalimumab treatment for patients with JIA-associated uveitis or CAU who have achieved corticosteroid-sparing control of inflammation on 12 consecutive months of adalimumab or a biosimilar treatment. Patients randomized to continue adalimumab treatment will receive the standard clinical practice weight-based dose of adalimumab. Patients in both arms will remain on their current dose of concomitant antimetabolite therapy if applicable. Further detail on dosing and administration of study treatment is provided in **Section 6.1.2**.

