7 STUDY INTERVENTION DISCONTINUATION AND PARTICIPANT DISCONTINUATION/ WITHDRAWAL

7.1 DISCONTINUATION OF STUDY INTERVENTION

Discontinuation of study treatment does not mean discontinuation from the study, and remaining study procedures should be completed as indicated in the study protocol. If a clinically significant finding is identified (including, but not limited to changes from baseline) after enrollment, the investigator or qualified designee will determine if any change in participant management is needed. Any new clinically relevant finding will be reported as an AE.

Discontinuation due to *efficacy*: Patients can discontinue the study treatment due to lack of efficacy and be declared a treatment failure if they have recurrence of ocular inflammation (≥ 2 -step increase in AC cell observed at 2 consecutive visits at least 7 days apart; $>0.5+$ AC cell for ≥ 28 days; $\geq 3+$ AC cell on a single visit; or $>0.5+$ vitreous haze, active retinal/choroidal lesions, or macular edema at a single visit) and/or recurrence of joint inflammation that is persistent and severe enough to necessitate unmasking to manage the arthritis recurrence. Patients with ocular inflammation that meets one of the treatment failure thresholds (see **Section 3.1**) should return for an evaluation to evaluate whether the increased inflammation is sustained (called the Treatment Failure visit), as close to the 7 or 28 day period as possible, but no earlier. Patients who meet the treatment failure threshold of ocular inflammation at Month 12 will be re-evaluated after the Month 12 visit to assess for sustained inflammation which would result in treatment failure. If inflammation is sustained at the follow-up visit, then treatment failure is declared. At this point, patients and doctors will be unmasked, and doctors can treat per best medical judgement. Patients in the placebo arm will be encouraged to restart adalimumab. The date of treatment failure is defined as the date of the initial visit when the ocular inflammation reached the threshold (see **Section 3.1**). A minimum of 90 days of follow-up is required following treatment failure, so if treatment failure is declared with fewer than 90 days remaining in the 12-month follow-up period, follow-up may be extended to up to 15 months. Regardless of the course of treatment pursued after treatment failure, all patients will be followed through Month 12 or a minimum of 90 days, whichever is longer.

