8.3 ADVERSE EVENTS AND SERIOUS ADVERSE EVENTS

8.3.1 DEFINITION OF ADVERSE EVENTS (AE)

Adverse event means any untoward medical occurrence associated with the use of an intervention in humans, whether or not considered intervention-related (21 CFR 312.32 (a)).

Examples* may include:

- Increased intraocular pressure (>24 mm Hg)
- Abnormal lab findings (≥ 2 times but < 5 times the upper limit of normal AST or ALT, rise in creatinine to ≥ 1.5 to < 2 mg/dL, reduction of white blood cell count to below 2500)
- Concurrent accident or illness
- Increase in the frequency and severity of symptoms of a pre-existing condition
- Side effects such as gastrointestinal upset, nausea, vomiting, fatigue

*Additional details on adverse event reporting are provided in the case report form: **Adverse Event Checklist**.

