7.2 Adverse Events

7.2.1 Individual Events

Adverse event reporting procedures are described fully in Protocol Section 8.3.² Non-serious adverse events are described in Protocol Section 8.3.1.² Serious non-ocular or ocular adverse events (which must be reported within 24 hours and which require a narrative form) are described in Protocol Section 8.3.2.² Adverse events will be reported in all presentations and publications.

Safety-related events that occurred at or before treatment failure with censoring at 6 months and then 12 months (two different groups of safety-related events) will be tabulated and reported. Descriptive tables of the number and frequency of adverse events will be broken down by treatment group, age, sex, antimetabolite use and known comorbidities. We will report total adverse events and serious adverse events, cross-tabulated by whether the adverse events were anticipated or unanticipated and by whether or not the adverse event led to discontinuation of medication.

We do not propose statistical evaluation of adverse events, since the study is not powered for such assessments.

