7.2.2 Pooled adverse events

Adverse events will be analyzed according to six main categories:

- Proportion of subjects with any ocular adverse event
- Proportion of subjects with any ocular serious adverse event
- Proportion of subjects with any systemic adverse event
- Proportion of subjects with any systemic serious adverse event
- Proportion of subjects with any laboratory adverse events
- Proportion of subjects with any laboratory serious adverse events

Note, hypothesis tests based on adverse events may be less than useful because the trial is not powered for these comparisons. These will only be provided to the DSMC if requested.

8 Reporting conventions

- All tables, data listings and figures will be presented in landscape orientation
- Direct annotation of figures will be preferred to legends. All figures with more than one variable or item will contain direct annotation
- Color will be used in figures only when needed to enhance clarity of communication

9 Appendix

All computations will be performed using the R statistical software ([R Core Team 2021](#)).³⁹ Specification of the random number seed and pseudorandom number algorithm determines the entire randomization assignment. Accordingly, the random number seed will be kept confidential.

10 References

2. [name]. *Adalimumab in Juvenile Idiopathic Arthritis-Associated Uveitis Stopping Trial (ADJUST)*.; 2019.

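### Nothing in the protocol or SAP keeps uveitis or arthritis recurrence out of the adverse event tables, so read literally the ocular AE figure partly restates the primary endpoint

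*Protocol*

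**What the plan says.** Three places in the protocol define AEs broadly enough to take in recurrence.

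- Section 8.3.1 gives as an example of an AE: "Increase in the frequency and severity of symptoms of a pre-existing condition".
- Section 8.3.4 sets conditions present at screening as baseline and continues: "However, if the study participant's condition deteriorates at any time during the study, it will be recorded as an AE". It also requires AEs to be documented whatever their relationship to treatment.
- Section 7.1, which also describes treatment failure, says: "Any new clinically relevant finding will be reported as an AE".

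The SAP adopts these rules. Section 7.2.1 says: "Adverse event reporting procedures are described fully in Protocol Section 8.3". It sets the reporting window as "Safety-related events that occurred at or before treatment failure with censoring at 6 months and then 12 months" and cross-tabulates AEs by whether they led to discontinuation. Section 7.2.2 lists six pooled summaries, including "Proportion of subjects with any ocular adverse event", with no exclusion for the disease under study.

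Protocol 4.1 hypothesises that "Patients randomized to continue treatment will have a higher rate of adverse events compared to patients randomized to stop treatment", and says that AE rates will be compared between groups. SAP 7.2.1 keeps the comparison descriptive.

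**The concern.** Every participant enters with a uveitis diagnosis, and those with JIA also have arthritis. A recurrence is a worsening of a condition present at entry, so the literal text makes it an AE. Protocol 3.1 and 7.1 date failure to the visit at which inflammation first reached the threshold. An AE with that onset date therefore lies inside a window that includes the failure date.

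The trial expects recurrence mainly to separate the arms in one direction (more and earlier on stopping) and AEs to separate them in the other (more on continuing). If recurrence is one of the AEs, a single row carries both effects and the larger one sets its sign. A clinician using the tables to judge whether stopping spares patients adverse events could not tell which effect was on view. Protocol 8.3.3.2 grades relatedness for each AE, but SAP 7.2.1 does not tabulate by it, so the planned tables would not separate the two.

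**Working it through.** **1. Reproduce the planning figure.** SAP 3.3.1 gives medians of 10 and 20 weeks, two-sided alpha 0.05, 88% power and 10% loss; follow-up is 48 weeks. The hazards are ln2/10 = 0.0693 (stop) and ln2/20 = 0.0347 (continue) per week. With φ(λ) = λ²/(1 − e^(−48λ)), the SAP formula gives 52.9 per arm, or 105.8 in total. Then 105.8/0.9 = 117.6, rounded up to 118, which agrees with the SAP.

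**2. Recurrence by arm.** f = 1 − e^(−λt).

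- 48 weeks: 96.4% stop, 81.1% continue (difference 15.4 points before rounding).
- 24 weeks: 81.1% stop, 56.5% continue (24.6 points).

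The 48-week figures imply about 105 failures in 118 patients before loss to follow-up, more than the 84 anticipated in SAP 3.7. So I also use the 12-month figure in SAP 3.3.2.1: 80% on stopping and, subtracting its 28-point detectable difference, 52% on continuing. That gives 59 × (0.80 + 0.52) = 78 failures. The 52% is derived from a detectable difference and is not an expected rate.

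**3. Add other ocular AEs.** The documents give no rates, so a is assumed: the 12-month probability of an ocular AE other than recurrence, independent of recurrence. A patient avoids the ocular row only by having neither event, so P(any ocular AE) = 1 − (1 − a)(1 − f).

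| Recurrence, stop / continue | Assumed a, stop / continue | True difference (continue − stop) | Any ocular AE, stop / continue | Shown difference (continue − stop) |
|---|---|---|---|---|
| 96.4 / 81.1 | 10 / 20 | +10 | 96.8 / 84.8 | −12 |
| 96.4 / 81.1 | 15 / 30 | +15 | 96.9 / 86.7 | −10 |
| 96.4 / 81.1 | 30 / 30 | 0 | 97.5 / 86.7 | −11 |
| 96.4 / 81.1 | 30 / 90 | +60 | 97.5 / 98.1 | +1 |
| 80 / 52 | 10 / 20 | +10 | 82.0 / 61.6 | −20 |
| 80 / 52 | 15 / 30 | +15 | 83.0 / 66.4 | −17 |
| 80 / 52 | 30 / 30 | 0 | 86.0 / 66.4 | −20 |
| 80 / 52 | 30 / 80 | +50 | 86.0 / 90.4 | +4 |

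**4. When the sign reverses.** A true excess on continuing is reversed when (1 − a_C)/(1 − a_S) > (1 − f_S)/(1 − f_C). The right side is 0.189 at the planning medians and 0.20/0.48 = 0.417 for 80/52. With a_S = 10%, the sign reverses for a_C above 10% and up to 1 − 0.189 × 0.9 = 83%, or 1 − 0.417 × 0.9 = 62.5%, respectively.

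**5. Does exclusion alone repair it?** No. Suppose the arms have the same hazard of other AEs, with 30% risk over 12 months, and exponential times. The hazards per 12 months are −ln0.70 = 0.357 for AEs, and −ln0.20 = 1.609 (stop) and −ln0.48 = 0.734 (continue) for failure. The crude proportion with an AE before failure is:

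- stop: 0.357/(0.357 + 1.609) × (1 − 0.20 × 0.70) = 15.6%;
- continue: 0.357/(0.357 + 0.734) × (1 − 0.48 × 0.70) = 21.7%.

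The 6-point excess on continuing is spurious: the stop arm leaves the window sooner. At the planning medians, mean time to failure or week 48 is 13.9 weeks (stop) against 23.4 weeks (continue).

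**The case against.** The strongest reply is that the documents do not show recurrences being recorded as AEs at all. Section 8.3.4 speaks of the participant's condition without naming uveitis. Recording is done on the Adverse Event Checklist, which is not among the documents, and the MOP is not available either. The protocol's structure also suggests a separation: 4.1 names recurrence rates and AE rates as two quantities, and 7.1 distinguishes discontinuation for efficacy from discontinuation for safety, stating that the latter is not treatment failure. This stands as far as it goes. A reader might infer that every recurrence does enter the ocular AE table; the documents do not establish that. But 7.1 classifies reasons for stopping treatment and does not exempt recurrence from AE recording, and no exemption appears elsewhere in the two documents.

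Other points also stand. Laboratory rows are untouched, and serious rows change only if a recurrence meets a seriousness criterion. SAP 3.1.3 separately compares discontinuation for intolerance and for safety. The DSMC receives outcomes beside AEs by arm (SAP 6.2.2), so it can see recurrences directly. Worsening after withdrawal is a real harm of stopping, and 4.1 does not say that its AE hypothesis means drug harm only. These points narrow the concern to a few summary rows. They argue for showing recurrence separately, not for hiding it.

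**Conclusion.** The point holds as a gap in definition with a foreseeable effect on descriptive safety figures. On the text alone, recurrence qualifies as an AE and falls inside the SAP window. It would then enter the ocular proportion, total AEs and AEs leading to discontinuation, and arthritis flares could enter the systemic row. At the planning medians recurrence alone puts the stop arm about 15 points higher at 48 weeks.

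A reader might conclude that the trial's AE comparison is reversed. The documents support only that it could be. Reversal rests on non-recurrence AE rates that they do not give, on independence, and on the Checklist and MOP containing no exemption. Under the assumed rates the sign reverses over a wide range and fails only when other ocular AEs are very common on continuing. The shown gap varies with the recurrence figures: for assumed AE rates of 15% and 30%, it is 10 points at the planning medians and 17 points at 80/52. No formal AE test is proposed and the primary efficacy analysis is not affected, so this is worth correcting but does not threaten the main result.

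**What to change.** In SAP 7.2.1 and 7.2.2:

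1. State whether protocol-defined uveitis and arthritis recurrence is recorded as an AE. If the Checklist or MOP already exempts it, cite the place.
2. Show recurrence on its own line by arm.
3. Report total, ocular and systemic AEs, and AEs leading to discontinuation, both excluding and including recurrence.
4. Give the recurrence-excluded figures as events per patient-year at risk, or as time to first event, and not only as crude proportions. Step 5 of the working shows why exclusion without this would mislead in the other direction.

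No new patient data are needed. Recurrences can be identified by matching AE dates to the treatment-failure and arthritis-flare data already collected. The match should allow for an AE dated at the confirming visit, since failure is dated to the initial one. The cost is SAP wording, a matching step and a few table rows. Because SAP version 5 was written after unmasking, the change should be dated in the revision history and labelled as made after the interim analysis. Showing both versions of each row leaves nothing to selective choice.

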8.3.5 ADVERSE EVENT REPORTING

Non-serious AEs will be reported through the **Adverse Event Checklist** at each follow-up visit, which will be submitted along with all other CRFs to the CC for review. Additional modes of reporting AEs are not required unless classified as an SAE.

8.3.6 SERIOUS ADVERSE EVENT REPORTING

The site investigator will immediately report any SAE/SUSAR to the sponsor regardless of relatedness to the study intervention. Reportable events include those listed in the protocol and must involve an assessment of the possibility that the study intervention caused the event. SAEs/SUSARs (e.g. all-cause mortality) must be reported in accordance with the protocol unless there is evidence suggesting a causal relationship between the study intervention and the event (e.g. death from anaphylaxis). In that case, the investigator must immediately report the event to the sponsor.

All SAEs/SUSARs will be followed until satisfactory resolution or until the site investigator deems the event to be chronic or the participant is stable. Other supporting documentation of the event may be requested by the CC or study sponsor and should be provided as soon as possible.

In case of an SAE/SUSAR, **Serious Adverse Event Narrative** will be completed by the Investigator and submitted to the Medical Monitor within 24 hours of study personnel learning of the SAE/SUSAR. Information recorded on this form will include the nature of the event, date of onset, date of resolution, date of notification to Medical Monitor, and action taken. The form will be reviewed and signed by the Medical Monitor. Any significant study drug-related adverse events will be reported by the Data and Safety Monitoring committee (DSMC) as appropriate. IRB offices should also be notified according to the policies of each institution.

The study sponsor will be responsible for notifying the Food and Drug Administration (FDA) of any unexpected fatal or life-threatening suspected adverse reaction as soon as possible, but in no case later than 7 calendar days after the sponsor's initial receipt of the information. In addition, the sponsor must notify FDA and all participating investigators in an Investigational New Drug (IND) safety report of potential serious risks, from clinical trials or any other source, as soon as possible, but in no case later than 15 calendar days after the sponsor determines that the information qualifies for reporting.

The study sponsor is also responsible for notifying the South Central – Berkshire Research Ethics Committee and the Medicines & Healthcare products Regulatory Agency (MHRA) of the fatal or life-threatening SAE/SUSAR as soon as possible, but no later than 7 days after the sponsor becomes aware. A CTIMPs Safety Report form should accompany the SAE/SUSAR notification to the main Research Ethics Committee. For non-fatal and non-life-threatening SAEs/SUSARs, the sponsor should inform the ethics committee and MHRA within 15 days after becoming aware. All SAEs, regardless of whether they originate in the UK or outside must be reported. The investigator at local UK sites where the SAE/SUSAR occurs is responsible for following local governance procedures, including notifying their Research & Development department.

8.3.7 REPORTING EVENTS TO PARTICIPANTS

If the rate or occurrence of AEs or SAEs changes the risk-benefit ratio for the trial or if new information becomes available that would impact the risk-benefit ratio or patients' willingness to participate in the trial, the CC will prepare a document with standardized language to communicate the information to study participants and IRBs. Study coordinators will provide the study document to participants and notify participants that they may contact the investigator if they have any questions regarding the new finding or change in risk-benefit ratio. Study coordinators will remind patients that participation in the trial is voluntary.

